2.1.2 Prior or concomitant medications

All medications will be coded using the World Health Organization-Drug Dictionary (WHO-DD) using the version currently in effect at Sanofi at the time of database lock.

- Prior medications are those the patient used 26 weeks prior to first investigational medicinal product (IMP) injection. Prior medications can be discontinued before first administration or can be ongoing during treatment phase.
- Concomitant medications are any treatments received by the patient concomitantly to the IMP, from randomization to the end of treatment. A given medication can be classified both as a prior medication and as a concomitant medication.

Acetaminophen (rescue medication) are permitted for causes other than target knee OA pain (eg, flu, headache, non- target joint pain) during the study, but must not be taken within 48 hours prior to a study visit, so as to not interfere with any patient-rated assessments. Information on acetaminophen will be captured in the eCRF and should include the date, medication strength, dose (eg, number of tablets per day), dosage form, and whether or not it was taken for target knee OA pain. On an as-needed basis in a tiered manner, the following therapies will be allowed as **rescue medication**: 1) Acetaminophen (500 mg), 2) Acetaminophen (325 mg)/oxycodone (5 mg), or 3) Acetaminophen (325 mg)/tramadol (37.5 mg).

Any technical details related to computation, dates, imputation for missing dates are described in [Section 2.5](#).

2.1.3 Efficacy endpoints

The baseline value for efficacy endpoints is defined as the last available value prior to the IMP administration or last available value on or before the date of randomization if not treated, unless otherwise specified.

WOMAC scores

The WOMAC NRS 3.1 questionnaire is a self-administered, health status measure used to probe symptoms of pain (WOMAC A), stiffness (WOMAC B), and function (WOMAC C) in patients with OA of the knee (1, 3). The questionnaire consists of 24 questions relating to the patient's assessment of his/her target joint pain (5 questions), stiffness (2 questions), and physical function (17 questions). An 11-point NRS ranging from 0 (None) to 10 (Extreme) will be used to capture the patient's response to each of the questions. All responses will be recorded directly on the paper patient questionnaire (PQ), and the PQ will serve as source documentation. The patient was asked to check the box that indicated his/her amount of target joint pain, amount of stiffness, and degree of difficulty completing tasks within the past 48 hours.

The WOMAC A consists of 5 questions assessing pain symptoms while walking, using stairs, at night while in bed, sitting or lying, and standing.

The WOMAC A1 is a single question within the WOMAC A that specifically assesses target knee pain while walking on a flat surface.

The WOMAC B consists of 2 questions assessing severity of stiffness that occurs after a period of inactivity later that same day.

The WOMAC C consists of 17 questions assessing physical function while performing the following activities: stair rise, rise from sitting, standing, bending, walking, getting in/out of a car, putting on/taking off socks, rising from bed, lying in bed, getting in/out of bath, sitting, getting on/off toilet, heavy household duties, and light household duties.

The WOMAC total score is computed as the sum of the available components of the 3 subscores: WOMAC A, WOMAC B and WOMAC C. The raw total WOMAC score ranges from 0 to 240, since the sums for the components of the 3 subscores range from 0 to 50 for the WOMAC A, 0 to 20 for the WOMAC B, and 0 to 170 for the WOMAC C. The total WOMAC score will be set to missing if any of the WOMAC subscores are set to missing as defined above. The raw total WOMAC score will be standardized to the 0 to 10 scale by dividing by 24.

Patient Global Self-Assessment (PTGA)

The patient's global self-assessment of target knee OA condition is the response on an 11-point NRS (0 = best possible to 10 = worst possible) to the question "Considering all the ways that the arthritis of your target knee affects you, select one response below for how you are doing at the present time." The patient's response will be recorded directly on the PQ, and the PQ will serve as the source documentation.

Clinical Observer Global Assessment (COGA)

The physician performs a global assessment of the patient's target knee OA using the 11-point NRS pain intensity rating scale (0 = best possible to 10 = worst possible) in response to the question "Considering all the ways that the arthritis of the patient's target knee affects him/her, select one response below for how you feel the patient is doing at the present time." The same physician will complete this assessment for all patients at a site and record in the eCRF and this will serve as the source documentation.

2.1.3.1 Primary efficacy endpoint(s)

The primary efficacy endpoint is change from baseline in WOMAC A1 over 26 weeks for hylan G-F 20 compared to placebo.

2.1.3.2 Secondary efficacy endpoint(s)

Secondary efficacy endpoints include the differences between treatment groups in:

- Change from baseline over 26 weeks in 7-day average walking pain score (measured by daily WOMAC A1, 7-day average WOMAC A1), WOMAC A, B, C and total, as well as PTGA, and COGA
- Percentages of positive responders over 26 weeks, where response is defined as a ≥ 2 -point improvement from baseline in the WOMAC A1 NRS

2.1.4 Safety endpoints

The safety analysis will be based on the reported adverse events and other safety information, including vital signs.

Observation period

The observation period will be divided into 2 periods:

- The pre-treatment period is defined as the time between when the patients give informed consent and the injection of IMP.
- The on-treatment period is defined as the time from the injection of the IMP up to Week 26 follow up visit.

The treatment-emergent adverse event period will only include the on-treatment period.

2.1.4.1 Adverse events variables

Adverse event observation period

- Pretreatment adverse events are adverse events that developed or worsened or became serious during the pretreatment period
- Treatment-emergent adverse events are adverse events that developed or worsened or became serious during the treatment-emergent adverse event period

All adverse events (including serious adverse events) will be coded to a lower-level term (LLT), preferred term (PT), high-level term (HLT), high-level group term (HLGT), and associated primary system organ class (SOC) using the version of Medical Dictionary for Regulatory Activities (MedDRA) currently in effect at Sanofi at the time of database lock.

Adverse event of special interest (AESI)

- Anaphylaxis
- Foreign Body Reaction
- Pseudosepsis
- Severe acute inflammatory reaction (SAIR)
- Joint infection
- Injection site allergy
- Drug allergy
- Pregnancy

2.1.4.2 Deaths

The deaths observation period are per the observation periods defined above.

- Death on-study: deaths occurring during the treatment-emergent adverse event period

2.1.4.3 Laboratory safety variables

Not applicable.

2.1.4.4 Vital signs variables

Vital signs include: temperature, heart rate, and systolic and diastolic blood pressure.

2.1.5 Tertiary efficacy endpoints and other endpoint

2.1.5.1 Tertiary efficacy endpoints

Tertiary efficacy endpoints include the differences between treatment groups in:

- Changes from baseline at Week 4, 8, 12, 16, 20, and 26 in 7-day average WOMAC A1
- Changes from baseline at Week 4, 8, 12, 16, 20, and 26 measured by WOMAC A1, WOMAC A, B, C and total, as well as PTGA and COGA
- The amount and days of permitted pain rescue medication use at Week 4, 8, 12, 16, 20, and 26.

2.1.5.2 Quality of life variables

Changes of quality of life from baseline at Week 4, 8, 12, 16, 20, and 26 in EQ-5D scores.

Patients' health status will be assessed using the EQ-5D-5L questionnaire which includes 5 levels of severity in each of the five dimensions: no problems, slight problems, moderate problems, severe problems, and extreme problems (4, 5).

2.2.1 Randomization and drug dispensing irregularities

Randomization and drug-dispensing irregularities occur whenever:

1. A randomization is not in accordance with the protocol-defined randomization method, such as a) an ineligible patient is randomized, b) a patient is randomized twice.

OR

2. A patient is dispensed an IMP kit not allocated by the protocol-defined randomization, such as a) a patient is dispensed a different treatment kit than as randomized (which may or may not contain the correct-as-randomized IMP), or b) a nonrandomized patient is treated with IMP reserved for randomized patients.

Randomization and drug-dispensing irregularities will be monitored throughout the study and reviewed on an ongoing basis.

All randomization and drug-dispensing irregularities will be documented in the clinical study report. If the number of irregularities is large enough to make a tabular summary useful, the irregularities will be categorized and summarized among randomized patients (number and percentages). Nonrandomized, treated patients will be described separately.

2.3 ANALYSIS POPULATIONS

Patients treated without being randomized will not be considered randomized and will not be included in any efficacy population.

The randomized population includes any patient who has been allocated to a randomized treatment regardless of whether the treatment kit was used.

For any patient randomized more than once, only the data associated with the first randomization will be used in any analysis population. The safety experience associated with any later randomization will be assessed separately.

The safety experience of patients treated and not randomized will be reported separately, and these patients will not be in the safety population.

2.3.1 Efficacy populations

2.3.1.1 Modified intent-to-treat population

The modified intent-to-treat population: mITT population contains all randomized and treated patients, as randomized. Patients will be analyzed in the treatment group to which they are randomized.

The mITT population is the primary analysis population and will be used for the analyses of all efficacy variables.

2.3.2 Safety population

The safety population is defined as:

- Randomized population who actually received at least 1 injection or part of an injection of Hylan G-F 20 or placebo. It is used for safety analysis, where observations will be summarized based on the treatment actually received

In addition:

- Nonrandomized but treated patients will not be part of the safety population; however, their safety data will be presented separately
- Randomized patients for whom it is unclear whether they took the IMP will be included in the safety population as randomized
- For patients receiving randomized more than once, the safety experience associated with any later randomization will be assessed separately.

2.3.3 Other analysis population

None.

2.4 STATISTICAL METHODS

Continuous data will be summarized using the number of available data, mean, standard deviation (SD), median, minimum, and maximum for each treatment group. Categorical and ordinal data will be summarized using the number and percentage of patients in each treatment group. Missing data will not be categorized in the summaries.

2.4.1 Demographics and baseline characteristics

Parameters will be summarized on the randomized population analyzed in the treatment group to which they were randomized. Analyses for the safety population will be included in the appendices if the size of the safety population is different (>10%) from the size of that in the primary analysis population for any treatment group.

Parameters described in [Section 2.1.1](#) will be summarized by treatment group and overall treatment groups using descriptive statistics.

Medical or surgical history as recorded on the eCRF will be summarized by SOC and PT.

P-values on demographic and baseline characteristic data will not be calculated.

2.4.2 Prior or concomitant medications

The prior and concomitant medications will be presented on the safety population.

Medications will be summarized by treatment group according to the WHO-DD dictionary, considering the first digit of the anatomic category (ATC) class (anatomic category) and the first 3 digits of the ATC class (therapeutic category). All ATC codes corresponding to a medication will be summarized, and patients will be counted once in each ATC category (anatomic or therapeutic) linked to the medication. Therefore patients may be counted several time for the same medication.

The table for prior medications will be sorted by decreasing frequency of ATC followed by all other therapeutic classes based on the overall incidence across treatment groups. In case of equal frequency regarding ATCs (anatomic or therapeutic categories), alphabetical order will be used.

The tables for concomitant medications will be sorted by decreasing frequency of ATC followed by all other therapeutic classes based on the incidence in the treatment group. In case of equal frequency regarding ATCs (anatomic or therapeutic categories), alphabetical order will be used.

2.4.3 Extent of investigational medicinal product exposure and compliance

The extent of IMP exposure will be assessed and summarized by actual treatment within the safety population ([Section 2.3.2](#)).

2.4.3.1 Extent of investigational medicinal product exposure

The extent of IMP exposure will be assessed by actual dose information.

Dose information will be summarized descriptively (number, mean, SD, median, minimum and maximum) for the volume administered of the IMP by treatment group.

Fluid or effusion withdrawn will also be summarized in a similar manner as dose information.

2.4.3.2 Compliance

No compliance analysis will be done for this study.

2.4.4 Analyses of efficacy endpoints

2.4.4.1 Analysis of primary efficacy endpoint(s)

The statistical test for the primary efficacy endpoint, the mean change from baseline measure of pain relief (WOMAC A1) between Hylan G-F 20 and placebo over 26 weeks, will be 2-sided at α level of 0.05.

For the primary efficacy endpoint, the following null hypothesis and alternative will be tested:

H0: Hylan G-F 20 is not superior to placebo

H1: Hylan G-F 20 is superior to placebo

The primary effectiveness analysis will be performed on the mITT population and will be based on repeated-measures Analysis of Covariance (ANCOVA) that will be used to test for differences in treatment efficacy, as quantified by the change from baseline in WOMAC A1 over 26 weeks between Hylan G-F 20 and placebo. The repeated measures ANCOVA model is equivalent to mixed model for repeated measures (MMRM) and will include terms for treatment, site, visit and visit-by-treatment interaction, as well as the baseline WOMAC A1 score as a covariate.

The difference between Hylan G-F 20 group and placebo group and its corresponding 95% confidence interval will be estimated within the framework of ANCOVA. An unstructured variance-covariance structure will be used to model the within-patient errors. If this model fails to converge, the following structures will be tested in this order: Toeplitz (equal variances and a separate correlation for each level of separation between the time points), AR (1) (first-order autoregressive, equal variances and exponentially decreasing correlations), CS (compound symmetry, equal variances and equal pairwise correlations across fixed time points). The first (co)variance structure yielding convergence will be used as the primary analysis.

The Kenward-Roger approximation will be used to estimate denominator degrees of freedom. Outcomes between patients are assumed to be independent. The primary comparison will be the contrast between Hylan G-F20 and control over 26 weeks. An example of the SAS code is provided below (note time is modeled with the visit variable):

SAS Display 1 Code for Continuous Endpoints

```
proc mixed data = data method = ml;
class patid randgrp site visit;
model y_chg = site baseline randgrp visit visit*randgrp / ddfm=kr;
repeated visit / type = un subject = patid;
lsmeans randgrp randgrp*visit / cl diff at baseline= baseline;
run;
```

where:

```
randgrp = Hylan G-F20, control
site     = site number
visit    = numerical visit weeks (4,8,12,16,20,26)
baseline= patient's baseline WOMAC A1 score
y_chg    = change from baseline WOMAC A1 value (WOMAC A1 value at post-baseline
          visit assessment minus the baseline value)
```

TYPE =

```
UN = unstructured covariance
CS = compound symmetry covariance
AR(1)= first-order autoregressive covariance
TOEP = Toeplitz covariance
```

Subgroup analysis

Descriptive analyses will be performed on the primary efficacy endpoint to summarize the treatment effects across subgroups for the following baseline characteristics as needed and will be considered as exploratory.

- Age groups (≤ 60 , > 60 years)
- BMI category (≤ 25 , > 25)
- Baseline WOMAC A1 score (5, 6-7, 8)

Sensitivity analysis

Sensitivity analyses will be performed using multiple imputation (MI) methods based on pattern mixture models (6) as appropriate.

First, a repeated measures Normal model will be fitted to the data using a Bayesian approach, with non-informative priors for the mean and variance-covariance matrix to provide a joint posterior for the parameters in the model. The repeated measures Normal model will include separate mean profiles for each treatment group and the same covariates as those in the primary analysis. Independent samples will then be drawn from the posterior distributions for the mean and variance-covariance matrix to provide inputs into an imputation model.

For each subject with missing data, these sampled values of the parameters for mean vectors and the variance-covariance matrices specify a joint distribution for their observed and unobserved outcome data. The post-withdrawal part of each pattern-specific distribution will be modelled using the approaches discussed below.

Based on this imputation model, a single set of data will be sampled for the missing data based on the distribution for the subject's missing data conditional upon their observed data.

Each imputed data set will then be analyzed using the same repeated measures analysis of ANCOVA and resulting treatment differences over 26 weeks and their standard errors will then be combined to produce valid statistical inference based on t-tests using the SAS PROC MIANALYZE. Least-squares mean change from baseline over 26 weeks for each treatment group will be calculated and displayed with their associated standard errors. Estimated treatment differences along with corresponding 95% confidence intervals and p-values will also be presented. These analyses will also be performed at each scheduled post-base visit.

The post-withdrawal part of each pattern-specific distribution will be modelled using the following approaches:

- **Missing at Random (MAR) Approach:** The means and variance-covariances following withdrawal are chosen to reflect the subject's own treatment group. This approach will provide similar results to using a mixed effects model where the unstructured covariance matrix is estimated separately for each treatment group.
- **Copy Reference (CR) Approach:** The whole distribution of Hylan G-F20 group even prior to withdrawal is assumed to be the same as the control group. This mimics the case where those withdrawing are in effect non-responders. If a patient on Hylan G-F20 is above the control group mean then this positive residual will feed through into subsequent observations, to a degree determined by the correlation in the control group. The patient's profile will slowly decay back towards the mean for the control group at later visits. For the control group, this is equivalent to the MAR approach above.

It is important to note that the CR approach is conservative and constructed to attenuate the treatment difference estimated from the primary analysis.

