1 OVERVIEW AND INVESTIGATIONAL PLAN

1.1 STUDY DESIGN AND RANDOMIZATION

This is a 26-week, multicenter, double-blind, randomized, placebo-controlled parallel group study to evaluate the efficacy and safety of a single dose of 6 mL of hylan G-F 20 (Synvisc-One) injected IA into the knee in Chinese patients with symptomatic OA of the knee.

A screening and wash-out period may last for up to 14 days, depending on the half-life of the medications (please refer to Appendix C of the protocol), followed by an 8-day baseline period including the treatment day (Day 1). Overall, up to 21 days are allowed between signing informed consent (at screening visit) and the randomization (Day 1). The study observation period starts at randomization and lasts until the end of the study. IMP or placebo will be injected IA into knee of the randomized patients on Day 1. Randomized patients who had either IMP or placebo will be invited for 7 post treatment observation visits, up to Week 26 (see Section 1.2).

The randomization ratio of hylan G-F 20: placebo is 1:1.

Approximately 422 patients (211 patients per treatment group) will be recruited and randomized.

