1.3 DETERMINATION OF SAMPLE SIZE

The sample size calculations are based on the primary efficacy variable of WOMAC A1 over 26 weeks, with the following assumptions:

- A common SD of [REDACTED] on the NRS scale
- [REDACTED] (on the NRS scale) mean difference in treatment effect of Hylan G-F 20 on the change from baseline in WOMAC A1 over 26 weeks, compared to placebo
- A t-test at a 2-sided 5% significance level with 90% power

The estimated treatment effect and SD are based on the observed treatment effect and SD for the WOMAC A1 over 26 weeks in US pivotal study (SOUND study) for a subgroup by excluding patients with symptomatic OA of another lower limb joint. Based on the above assumptions, 211 patients per treatment group, thus 422 patients in total will be randomized for this study.

As the ANCOVA model will be used for primary analysis, the power should be somewhat higher due to reduced estimate variability versus the t-test.

Calculations were made using nQuery Advisor 6.01.

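### If both the unstructured and Toeplitz models fail, the primary test falls to AR(1) before CS with model-based errors, and its type I error could be about 5% to 11%, depending on a correlation pattern the documents do not give

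*SAP*

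**What the plan says.** SAP 2.4.4.1 sets the primary test, which "will be 2-sided at α level of 0.05", on a repeated-measures model with treatment, site, visit, visit-by-treatment and baseline WOMAC A1. The visits are Weeks 4, 8, 12, 16, 20 and 26. The primary comparison is the treatment difference averaged over them.

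The within-patient covariance is unstructured. If that model does not converge, the order is Toeplitz, then AR(1), then CS, and convergence alone decides: "The first (co)variance structure yielding convergence will be used as the primary analysis". On inference the section adds: "The Kenward-Roger approximation will be used to estimate denominator degrees of freedom". The sample code has `method = ml`, `ddfm=kr` and no `EMPIRICAL` option, so standard errors come from the fitted structure.

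SAP 2.4.4.2 uses the same model for 7-day average WOMAC A1, WOMAC A, PTGA and COGA. These are four of the five endpoints in the Hochberg family. SAP 2.5.7, on statistical technical issues, is marked not applicable, so it adds no safeguard.

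**The concern.** The variance of a six-visit mean depends on the sum of all 36 entries of the covariance matrix. CS reproduces the average variance and the average covariance, so with complete data it gets that sum right whatever the true pattern. AR(1) is driven by the correlation between neighbouring visits and extrapolates it geometrically. If the true correlation flattens out, AR(1) makes the distant pairs too weakly correlated, the sum too small and the standard error too small.

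Kenward-Roger corrects for small-sample uncertainty within the chosen structure; it does not repair a wrong one. If AR(1) became the primary analysis under such a pattern, the 5% test would be anticonservative and the 95% interval too narrow. CS, the simpler structure that would protect this contrast, comes after AR(1) and would never be reached once AR(1) converged.

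**Working it through.** **The plan's own figure.** SAP 1.3 assumes "A t-test at a 2-sided 5% significance level with 90% power" and concludes that "211 patients per treatment group, thus 422 patients in total will be randomized for this study". The SD and difference are redacted, so the number cannot be rebuilt independently. As a consistency check only, 211 per group at 90% power implies a difference/SD of 0.316. The plan states no type I error for the fallback models beyond the nominal 0.05, so that is the figure tested below.

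**Inputs from the documents.** Six visits, the equally weighted contrast, the fallback order, model-based errors, two-sided 5%, 422 patients allocated 1:1.

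**Inputs assumed.** The true correlation pattern, which the documents do not give and which is varied below; dropout of 0% or 15%; 20 sites in the simulation.

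**Formula.** Let S be the true 6×6 matrix and V the large-sample maximum-likelihood fit under the working structure. The ratio of reported to true standard error is R = √(sum of V / sum of S), and the type I error is 2 × [1 − Φ(1.96 × R)]. For equal variances and a constant correlation r between neighbouring visits, the AR(1) fit recovers the variance and r exactly. Hence, with unit variances:

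sum of V = 6 + 2(5r + 4r² + 3r³ + 2r⁴ + r⁵).

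**Equal correlation.** Here the sum of S is 6 + 30r. For r = 0.5, sum of V = 6 + 2(2.5 + 1 + 0.375 + 0.125 + 0.031) = 14.06 and sum of S = 21. So R = √(14.06/21) = 0.818, and the type I error is 2 × [1 − Φ(1.603)] = 10.9%.

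| True equal correlation | Sum of V, AR(1) | Sum of S | R | Type I error |
|---|---|---|---|---|
| 0.3 | 9.92 | 15 | 0.813 | 11.1% |
| 0.4 | 11.79 | 18 | 0.809 | 11.3% |
| 0.5 | 14.06 | 21 | 0.818 | 10.9% |
| 0.6 | 16.85 | 24 | 0.838 | 10.1% |
| 0.7 | 20.27 | 27 | 0.867 | 8.9% |
| 0.8 | 24.49 | 30 | 0.903 | 7.7% |

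**Slow decline.** If correlation falls linearly from 0.7 at lag 1 to 0.4 at lag 5, sum of S = 6 + 2(5×0.7 + 4×0.625 + 3×0.55 + 2×0.475 + 0.4) = 24. The AR(1) fit again has r = 0.7, so sum of V = 20.27, R = 0.919 and the type I error is 7.2%. Other linear declines gave 6.2% to 8.6%.

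**Other patterns under an AR(1) fit**
- Random intercept plus AR(1): 5.5% to 6.5%.
- AR(1) plus measurement noise, with or without a random intercept: 6.7% to 8.5%.
- True AR(1) by visit: 5.0%.
- Exponential decay in actual weeks, which isolates the six-week gap from Week 20 to Week 26: 5.1%.

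**Same truths, other fitted structures.** Large-sample type I error with complete data is 5.0% for CS and 4.9% to 5.1% for Toeplitz.

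**Simulation.** 422 patients, baseline covariate, maximum likelihood, 1,000 runs per cell, Monte Carlo standard error about 0.7 points at 5%. It used plain model-based errors without the Kenward-Roger step, so AR(1) is best read against CS in the same row.

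| Truth | AR(1) fit, 0% / 15% dropout | CS fit, 0% / 15% dropout |
|---|---|---|
| Equal, 0.5 | 11.5% / 10.1% | 6.3% / 5.4% |
| Equal, 0.7 | 9.3% / 10.0% | 4.1% / 5.4% |
| Linear, 0.7 to 0.4 | 6.7% / 8.9% | 4.9% / 6.8% |
| Random intercept 0.4 plus AR(1) 0.5 | 8.5% / 7.4% | 6.6% / 6.1% |
| AR(1), 0.7 | 5.8% / 6.0% | 5.7% / 6.3% |

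**How likely the branch is.** With 15% dropout under two of these truths, the unstructured model converged in 600 of 600 runs and Toeplitz in 120 of 120. These runs used normal data and a purpose-written routine rather than PROC MIXED, so they are indicative only.

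**Single-visit contrasts.** With complete data and equal variances the AR(1) fit recovers the marginal variance, so the type I error at any one visit is 5.0% under every equal-variance pattern tried.

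**The case against.** The chain is fixed in advance, begins with the least restrictive structure and leaves the analyst no data-driven choice. Nothing in the documents suggests that the unstructured model will struggle with six visits and this sample size. AR(1) is a third-level contingency, and the size of the problem rests on a correlation that has to be assumed. All of this stands. It makes the point minor but does not make the order sound.

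Four stronger readings are tempting, and the documents do not support them.
- A reader might infer that failure of the unstructured model alone inflates the error. It does not: Toeplitz comes next and holds about 5%.
- A reader might take 7% to 11% as the size. That covers mainly equal or slowly falling correlation. If AR(1) is close to true, the error is close to 5%.
- A reader might extend the problem to the tertiary endpoints. Those are changes at individual visits, reported as exploratory, and the mechanism belongs to time-averaged contrasts.
- A reader might blame the unequal last interval. Under exponential decay in weeks it adds only about 0.1 point.

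**Conclusion.** The point holds as a conditional weakness of low priority. If the unstructured and Toeplitz models both fail and AR(1) converges, the primary test and the four continuous secondary tests would have a type I error between about 5% and 11%. In every pattern computed, a departure from 5% was towards false positives. The corresponding coverage of the nominal 95% interval is about 95% down to 89%.

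This rests on assumed correlation patterns, large-sample fits with complete data, and simulations at 0% and 15% dropout. The probability of reaching the branch cannot be taken from the documents but looks small. The planned unstructured analysis is not called into question.

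**What to change.** In SAP 2.4.4.1, replace the fallback paragraph with a fixed sequence:
1. If the unstructured model does not converge, refit the same structure in Cholesky form (`TYPE=FA0(6)`) or from other specified starting values.
2. If that fails, use Toeplitz.
3. If that fails, use CS. Delete AR(1), or place it after CS.
4. For any structured fallback, use empirical (sandwich) standard errors with between-within degrees of freedom.

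The cost is SAP wording only. It needs no new data and changes nothing if the unstructured model converges. Two limits should be stated. Kenward-Roger would not be used on the fallback branch. Under missing-at-random dropout a simplified covariance can still shift the estimate slightly, which a sandwich variance does not repair. The benefit of trying CS before AR(1) was computed above; the sandwich step was not.
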